#### **12.6.4 Menstrual Cycle**

Age of menarche, length of the menstrual cycle and menstrual cycle regularity will be summarized for girls by lead-in study and lead-in treatment.

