
• Primary objective:
– to evaluate the long-term safety and tolerability of vortioxetine in child and adolescent patients with a DSM-5™/diagnosis of MDD• Secondary objectives:
– to evaluate the long-term effectiveness of flexible doses of vortioxetine in a range of 5 mg/day to 20 mg/day on:
• depressive symptoms• clinical global impression• cognitive function• functionality		
Study Methodology		

• Interventional, multi-national, multi-site, open-label, flexible-dose, long-term extension study in child and adolescent patients with MDD who completed one of the double-blind, placebo-controlled, active-reference studies 12709A and 12710A.• The Baseline Visit of this extension study hereafter referred to as Baseline Extension A, will be Visit 12 (Completion Visit) of lead-in Study 12709A or 12710A.• The dosage of vortioxetine will be initiated at 5 mg/day for the first 2 days prior to receiving 10 mg/day.• The target dose is 10 mg/day; however the investigator has the possibility to adjust the dose in case of unsatisfactory response up to 20 mg or in case of dose-limiting adverse events. The dose can be up or down titrated with 5 mg/day. The patient should receive the same dose for 2 days before being up-titrated to a new dose. Changes in dosing may occur at any site visit during the treatment course at the investigator's discretion but the maximum dose may not exceed 20 mg/day.• The treatment period is 26 weeks. The total study duration per patient from Baseline Extension A to the end of follow-up will be approximately 30 weeks.• If possible, patients who withdraw are to be seen for a withdrawal visit as soon as possible and they will be contacted for a safety follow-up visit 4 weeks after withdrawal.• The study design is presented in Panel 1 and the scheduled assessments are summarised in Panel 2.• Investigators will not be informed about which treatment their patients received during the 12709A or 12710A study at the time of enrolling them into this open-label extension study.• For ethical and equity reasons patients who turned 18 years during the lead-in study 12710A can be enrolled into this extension study.		

Target Patient Population

- The patient is a male or female, child aged ≥ 7 and < 12 years or adolescent aged ≥ 12 and ≤ 18 years at Baseline Extension A.

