- The patient must have completed Study 12709A or 12710A (Visit 12, Completion Visit) immediately prior to enrolment into this extension study.
- The patient had a primary diagnosis of a Major Depressive Disorder (MDD) at entry in study 12709A or 12710A, diagnosed according to DSM-5™.
- The patient is indicated for long-term treatment with vortioxetine according to the clinical opinion of the investigator.

Investigational Medicinal Products, Doses and Mode of Administration

- Vortioxetine – 5 mg/day, tablets, orally
- Vortioxetine – 10 mg/day, tablets, orally
- Vortioxetine – 15 mg/day, tablets, orally
- Vortioxetine – 20 mg/day, tablets, orally

The treatment should be given once a day, preferably in the morning.

Efficacy Assessments

- Assessment of depressive symptoms:
 - Investigator rated
 - Children Depression Rating Scale Revised version (CDRS-R)
- Assessment of Global Impression:
 - Investigator rated
 - Clinical Global Impression Scale – Severity of Illness (CGI-S)
 - Clinical Global Impression Scale – Global Improvement (CGI-I)
- Assessment of cognitive function:
 - Parent rated (children aged 7-11 years at Baseline Extension A)
 - Behaviour Rating Inventory of Executive Function (BRIEF) – Global Executive Composite (overall summary score) – Subscales (initiate, working memory, plan/organize, organization of materials, monitor, inhibit, shift and emotional control)
 - BRIEF – Metacognition Index – Subscales (initiate, working memory, plan/organize, self-monitor, organization of materials)
 - Patient rated (adolescents aged 12-18 years at Baseline Extension A)
 - Behaviour Rating Inventory of Executive Function – Adolescent version- (BRIEF-SR) – Global Executive Composite (overall summary score) – Subscales (working memory, plan/organize, organization of materials, task completion, monitor, inhibit, shift and emotional control)
 - BRIEF-SR – Metacognition Index – Subscales (working memory, plan/organize, organization of materials and task completion)
- Assessment of functionality:
 - Investigator rated
 - Children's Global Assessment Scale (CGAS)
 - Patient rated
 - The PedsQL Present Functioning Visual Analogue Scales (PedsQL VAS)

Safety Assessments

- Adverse Events (AEs)
- Paediatric Adverse Event Rating Scale (PAERS)
- Clinical safety laboratory tests, including reproductive hormones
- Vital signs
- Menstrual cycle (age of menarche, the length of the menstrual cycle)
- Weight/Height
- Electrocardiograms (ECGs)

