3.1 Overview of the Study Design

This study has been designed in accordance with the *Declaration of Helsinki*.¹⁹

This is an interventional, multi-national, multi-site, open-label, flexible-dose, long-term extension study in child and adolescent patients with MDD who completed one of the double-blind, placebo-controlled, active-reference Studies 12709A and 12710A.

This study will be conducted in compliance with the protocol, *Good Clinical Practice*,²⁰ and applicable regulatory requirements.

An overview of the study is presented in [Panel 1](#).

The Baseline Visit of this extension study, hereafter referred to as Baseline Extension A, will be Visit 12 (Completion Visit) of lead-in Study 12709A or 12710A.

The dosage of vortioxetine will be initiated at 5 mg/day for the first 2 days prior to receiving 10 mg/day.

The target dose is 10 mg/day; however the investigator has the possibility to adjust the dose in case of unsatisfactory response up to 20 mg or in case of dose-limiting adverse events. The dose can be up or down titrated with 5 mg/day. The patient should receive the same dose for 2 days before being up-titrated to a new dose. Changes in dosing may occur at any site visit during the treatment course at the investigator's discretion but the maximum dose may not exceed 20 mg/day.

The treatment period is 26 weeks. The total study duration per patient from Baseline Extension A to the end of follow-up will be approximately 30 weeks.

If possible, patients who withdraw are to be seen for a withdrawal visit as soon as possible and they will be contacted for a safety follow-up visit 4 weeks after withdrawal.

Investigators will not be informed about which treatment their patients received during the 12709A or 12710A study at the time of enrolling them into this open-label extension study.

For ethical and equity reasons patients who turned 18 years during the lead-in study 12710A can be enrolled into this extension study.

Approximately 850 patients at approximately 120 sites from 12709A and 12710A are planned for enrolment.

An independent Data Monitoring Committee will be established in order to review the safety and tolerability data throughout this study. The same DMC will cover all the clinical studies in the pediatric vortioxetine program.

An internal safety committee at H. Lundbeck A/S has been set up for vortioxetine, who will perform regular evaluations of blinded safety data.

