9.4.5 Menstrual Cycle

The following will be recorded:

- Age of menarche
- The length of the menstrual cycle (number of days from the first day of menstruation to the day before the first day of the next menstrual period)
- Menstrual cycle regularity

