17.10.2 Analyses of Safety Endpoints

Adverse events, PAERS items, Tanner scores, clinical safety laboratory tests, vital signs, height, weight, BMI, and ECG parameters will be summarised, and observed potentially clinically significant (PCS) safety laboratory test values will be flagged and summarised. Length of menstrual cycle and C-SSRS scores will be summarised using descriptive statistics.

For variables that are heavily dependent on sex and age (such as Tanner and menstrual cycle length) further exploratory descriptions will be made.

Analyses will be performed with respect to the baseline in lead-in study 12709A or 12710A and Baseline Extension A.

For exploratory use a random effects slope and intercept model will be applied using Mixed Model Repeated Measurements (MMRM) to study long-term development in safety parameters such as weight.

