## 5 Descriptive Statistics

Unless otherwise specified, summary statistics (n, arithmetic mean, standard deviation [SD], median, lower and upper quartiles, minimum and maximum values) will be presented for continuous variables, and counts and, if relevant, percentages will be presented for categorical variables.

Furthermore, and unless otherwise specified, the data will be summarised for all patients, and by lead-in study and by lead-in treatment, respectively.

Lastly, and unless otherwise specified, data listings will include site, lead-in study, patient number, sex, age, race, and weight at OLEXA.

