## 12.2 General Methodology for Other Safety Data

Unless otherwise specified, tables, graphs, and listings will be based on the APTS, and the tables will be presented for all patients and by lead-in study and by lead-in treatment.

The denominators for the summaries of a given variable will be based on the number of patients with non-missing values at a given visit or during the assessment period.

Descriptive statistics for the safety variables, both absolute values and change from baselines (baseline at randomisation in lead-in study and OLEXA), will be presented by visit and for the last assessment. All available post-OLEXA assessments will be included in the identification of the last assessment.

The number and percentage of patients with at least one PCS value at any post-baseline assessment time point will be summarized by variable. All available assessments will be included in the evaluation of PCS values.

The number and percentage of patients with values out-of-reference range and/or PCS range will be summarized by variable, visit, and last post-baseline assessment.

For patients with post-baseline PCS values, listings will be provided including all the values for those patients for the variable, with flagging of PCS values and out-of-reference-range values.

The PCS definition will be provided by H. Lundbeck and are stated in [Appendix IV](#).

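### Age of menarche is summarised only from girls already past menarche, so the summary is truncated by current age, mostly reflects pre-study events in adolescents, and is insensitive to a delay

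*SAP*

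**What the plan says.** SAP 12.6.4 is a single sentence: "Age of menarche, length of the menstrual cycle and menstrual cycle regularity will be summarized for girls by lead-in study and lead-in treatment". SAP 12.2 sets the general rule for such variables: "The denominators for the summaries of a given variable will be based on the number of patients with non-missing values at a given visit". By default, SAP 5 also adds an overall column: "the data will be summarised for all patients, and by lead-in study and by lead-in treatment, respectively".

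Protocol 9.4.5 lists what is recorded: age of menarche, cycle length and cycle regularity. It describes no item for whether menarche has been reached. The flow chart (SAP Appendix II, Table 1) schedules the menstrual assessment at Visits 1, 9 and 13. The population is a "child aged ≥ 7 and < 12 years or adolescent aged ≥ 12 and ≤ 18 years at Baseline Extension A", so girls before and after menarche are mixed. Protocol 3.1 adds: "The treatment period is 26 weeks".

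Two further places matter. Protocol 17.10.2 promises: "For variables that are heavily dependent on sex and age (such as Tanner and menstrual cycle length) further exploratory descriptions will be made". The SAP specifies no such description for menstrual data, and SAP 17 does not list its removal. The endpoint lists in Protocol 16.1 and SAP 3.1 name cycle length only. Age of menarche appears as a safety assessment in the protocol synopsis.

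**The concern.** A girl has no age of menarche until menarche occurs. The SAP does not say in words that pre-menarcheal girls are left out, but it follows from the nature of the variable and from the non-missing denominator. Three things result.

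- No recorded value can exceed the girl's age at her last visit, so the youngest girls contribute only early values.
- Any menarche before study treatment cannot reflect that treatment. Most adolescent values will be of this kind.
- A delay acts on the mean in two opposing ways. Fewer late values enter, which lowers it, and those that do enter are later, which raises it.

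No section plans a count of pre-menarcheal girls, a split by age, or a split of pre-study from in-study menarche. In a study whose primary objective is long-term paediatric safety, the table could be taken as information on pubertal timing when it carries almost none.

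**Working it through.** The documents give no figure for menarche, so there is none to reproduce. The size has to be illustrated.

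**Inputs from the documents.** Ages 7 to 18 at OLEXA; 26 weeks of treatment (0.5 year); about 850 patients planned (Protocol 17.12).

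**Assumptions not in the documents.** Natural age of menarche T is normal with mean 12.5 (range 12.0-13.0) and SD 1.2 (range 1.0-1.4). Age a at OLEXA is uniform within the band. Only girls pre-menarcheal at OLEXA can be delayed, by d = 0.25 year.

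**Formulas.** A girl has a pre-study value if T ≤ a. She has a new value, recorded as T + d, if a < T ≤ a + 0.5 − d. The planned mean averages both kinds of value. The new-menarche percentage is P(a < T ≤ a + 0.5 − d) / P(T > a), with numerator and denominator each averaged over a.

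**Ages 7-12.** Before OLEXA 5.39% have a value, with mean 10.69.
- No delay: 4.18% new, mean 11.39. Planned mean = (5.39 × 10.69 + 4.18 × 11.39) / 9.57 = 11.00. New menarche = 4.18 / 94.61 = 4.4%.
- Delay: 1.89% new, mean 11.55. Planned mean = (5.39 × 10.69 + 1.89 × 11.55) / 7.28 = 10.91. New menarche = 1.89 / 94.61 = 2.0%.

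**Ages 12-18.** Before OLEXA 87.17% have a value, with mean 12.32.
- No delay: 4.85% new, mean 13.30. Planned mean = (87.17 × 12.32 + 4.85 × 13.30) / 92.02 = 12.37. New menarche = 4.85 / 12.83 = 38%.
- Delay: 2.59% new, mean 13.48. Planned mean = (87.17 × 12.32 + 2.59 × 13.48) / 89.76 = 12.35. New menarche = 2.59 / 12.83 = 20%.

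**Ages 7-18 pooled.** The mean is 12.26 with and without the delay.

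**Ranges over the assumption sets, same delay.**

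| Ages | Change in planned mean (years) | New menarche, no delay | New menarche, delay |
|---|---|---|---|
| 7-12 | −0.07 to −0.09 | 2.7% to 6.4% | 1.2% to 3.0% |
| 12-18 | −0.01 to −0.02 | 32% to 44% | 17% to 24% |
| 7-18 pooled | −0.003 to +0.004 | | |

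**Age artefact.** With no drug effect the two bands already differ by 12.37 − 11.00 = 1.37 years (1.15 to 1.63 over the ranges).

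**Precision.** Suppose a quarter of the 850 are girls in each age band (212; an assumption).
- Ages 7-12: 212 × 0.0957 ≈ 20 values. With SD 0.79 the standard error is 0.79 / √20 = 0.18 year, against a shift of 0.09.
- Ages 12-18: 212 × 0.920 ≈ 195 values. With SD 1.14 it is 1.14 / √195 = 0.08 year, against a shift of 0.02.

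The expected number of new menarches would be about 9 falling to 4 in the younger band, and about 10 falling to 5 or 6 in the older.

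**The case against.** Several objections stand and limit the point. Age of menarche is not a listed endpoint, and nothing says it will be used to look for delay. Other pubertal readouts exist: Tanner shift tables by sex (SAP 12.6.3), the hormone panel (Protocol 9.4.2) and puberty terms in the adverse event search (SAP Panel 5). SAP 5 gives n, median, quartiles and range as well as the mean, so the number of girls with a value will be visible. Protocol 17.10.2 leaves room for more, although an unspecified promise does not supply the missing table. All patients receive vortioxetine in the extension, so no replacement can attribute a delay to the drug either, and the events will be few.

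A reader might infer more: that a delay would make the recorded mean fall, so that the table would point to earlier puberty. That does not hold in general. Within an age band the mean fell in every case tested from OLEXA over 26 weeks, but by hundredths of a year for modest delays. Pooled over 7-18, delays of 0.05 to 0.1 year raised it slightly, by about 0.001 to 0.004 year. Even at ages 7-12 it can rise: with SD 1.0 and a delay starting at lead-in entry (12 + 26 = 38 weeks), it goes from 11.373 to 11.376 for a 0.1-year delay. Starting the delay there also gives larger effects, but the lead-in studies were placebo-controlled with an active reference, so common exposure starts only at OLEXA.

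A reader might also take the gap between lead-in studies as certain. That 12709A enrolled children and 12710A adolescents is inferred, for example from the provision for patients who turned 18 during 12710A. It is not stated outright.

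**Conclusion.** The point holds as one of insensitivity and age truncation, not of a dependable reversal of sign. The planned summary describes girls already past menarche. In adolescents about 87% had reached it before OLEXA under the base assumptions. If the lead-in studies enrolled different age groups, a by-study table would show a gap of more than a year with no drug effect. A 0.25-year delay shifts the mean by less than 0.1 year, below its standard error under the assumed numbers, while the new-menarche percentage roughly halves. These sizes rest on an assumed menarche distribution and uniform ages. The truncation itself does not depend on them. Severity is minor.

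**What to change.** In SAP 12.6.4, treat pre-study age of menarche as a baseline characteristic only. For safety, report:

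- (a) the number of girls pre- and post-menarcheal at OLEXA, by age;
- (b) among girls pre-menarcheal at OLEXA, the number and percentage with new menarche by completion or withdrawal, by age.

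This would also give content to the commitment in Protocol 17.10.2. First confirm that the database separates menarche not yet reached from a missing answer, since Protocol 9.4.5 describes no status item. A time-to-menarche curve on the age scale is optional, and would also need age of menarche recorded finely enough.

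The cost is SAP wording and one small descriptive table from assessments already scheduled at Visits 1, 9 and 13, provided the status can be recovered. The table will have few events in the youngest girls and no untreated comparator, and its text should say so.

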#### **12.6.5 Remote Visits**

Patients with remote visits will be listed.

### **13 Pharmacokinetic/Pharmacodynamic Analyses**

A separate analysis plan for pharmacokinetic/pharmacodynamic analyses will be prepared by Quantitative Pharmacology, H. Lundbeck A/S.

### **14 Interim Analyses**

No interim analyses for efficacy are planned.

An independent Data Monitoring Committee was established in order to review the safety and tolerability data throughout the study. The same Data Monitoring Committee (DMC) will cover all the clinical studies in the paediatric vortioxetine program. DMC includes child and adolescent psychiatrists. The DMC ensures that the ethical principles are observed and monitors the safety of the patients. The DMC will be informed to what extent the data and analyses provided to them have been quality controlled. Members of the DMC will not be involved in other study-related tasks. The details of the DMC procedures are described in the Data Monitoring Committee Charter.

A CRO is contracted to perform the analyses for the DMC.

### **15 Sample Size Considerations**

No sample size calculation has been performed for the present study, which just includes patients who have completed the studies 12709A or 12710A and are eligible for enrolment for this study.

It is expected that some 15-20% of the 1200 patients randomised to the lead-in studies will drop out and that a maximum of 85% of these “lead-in completers” are expected to accept to continue into this extension study. This gives approximately 850 patients.

### **16 Statistical Software**

The statistical software used will be SAS®, Version 9.4 or later.

## 17 Changes to Analyses Specified in the Protocol

The following changes have been made as compared to the latest version of the protocol:

- C-SSRS categorisation has been updated and will no longer include C-CASA.
- Treatment emergent adverse events (TEAE) in 12712A is defined as an adverse event that starts or increases in intensity or seriousness after visit 1 of study 12712A.
- The analyses regarding time to first relapse and time to first loss of remission have been removed
- The analysis of random slope and intercept has been removed

## 18 Details on Data Handling

### 18.1 Definition of Baseline and Period

OLEXA will be Visit 1 in 12712A for assessments *not* included in 12709A or 12710A. For assessments *included* study in 12709A or 12710A, Visit 12 in either 12709A or 12710A will otherwise serve as OLEXA.

No baseline in 12712A is defined for the C-SSRS.

### 18.2 Derived Variables

#### 18.2.1 Behavioural Rating Inventory of Executive Function® (BRIEF®)

BRIEF (parent) form was used for children aged 7-11 and contains 86 items, the BRIEF-SR (self-reported) form was used for adolescents aged 12-18 and contains 80 items. Items are rated on a 3-point scale, with 1 corresponding to Never, 2 corresponding to Sometimes, and 3 corresponding to Often. These items cover 8 non-overlapping clinical scales (Panel 7). For BRIEF (parent) form, only the first 72 items will be included in the clinical scales.

The clinical scales combine to form two Indexes, the Behavioural Regulation Index (BRI) and the Metacognition Index (MI), and one composite summary score, the Global Executive Composite (GEC), which is a summary score that incorporates all eight clinical scales.

For BRIEF (parent), the Metacognition Index (MI) is comprised of Initiate, Working Memory, Plan/Organize, Organization of Materials, and Monitor scales. For BRIEF-SR, the Metacognition Index (MI) is comprised of Working Memory, Plan/Organize, Organization of Materials, and Task Completion.

For each clinical scale, the scale raw score is calculated as the sum of its item scores, and then converted to T-score based on the conversion table. The index (BRI and MI) scores are calculated as the sum of the corresponding scale T-scores, and, was converted to index T-

scores based on the conversion table. GEC score was then calculated as the sum of the index scores and converted to T scores based on the conversion Table.

If the total number of missing items that contribute to the calculation of total score (GEC) is greater than 14, then the total score will not be calculated. Similarly, if more than two items that contribute to the calculation of a scale score are missing, then the scale score should not be calculated for that scale. Otherwise, missing responses for one or two items that contribute to a scale score should be assigned a score of 1 when calculating the scale score.

If a patient used a wrong form at some visit, data from this visit would be excluded from the analysis. If a patient used a wrong form at the baseline visit, this patient will be excluded from the analysis of BRIEF scales.

### Panel 7 Clinical Scales of BRIEF

BRIEF (Parent)		BRIEF-SR	
Clinical Scales	Number of items	Clinical Scales	Number of items
Inhibit	10	Inhibit	13
Shift	8	Shift	10
Emotional Control	10	Emotional Control	10
Initiate	8	Monitor	5
Working Memory	10	Working Memory	12
Plan/ Organize	12	Plan/ Organize	13
Organization of Materials	6	Organization of Materials	7
Monitor	8	Task Completion	10

